### 18.4 Reimbursement or compensation to study participants

Patients obtaining medication abortion who participate in the study will be reimbursed \$25 for completing each of the two surveys, for a maximum reimbursement of \$50. Reimbursement will be in the form of an online Amazon gift card. Patients' medication abortion procedure and medications will also be paid for by the study. At Planned Parenthood Tacoma, participants will be offered a \$25 travel remuneration to compensate them for time and costs associated with travel to the study pharmacy. This is the only study pharmacy that is not located at the same site as the study clinic.

Pharmacists will be reimbursed \$25 for completing the surveys, and another \$25 if the interview is completed. Both the survey and interview may be completed at baseline (before the study is initiated) and at the end of the study, for a maximum reimbursement of \$100. Reimbursement will be in the form of an online Amazon gift card.

Each pharmacy will be reimbursed \$18 for each dose of Mifeprex® and misoprostol that is dispensed. Since Mifeprex® is not generally a covered benefit for pharmacy dispensing, we do not anticipate that pharmacies will be able to bill insurances for their standard dispensing fee, so this will be provided as part of the study.

The study will cover the cost of the medication abortion services for all participants at UCSF, UC Davis, and UCSD. The study will cover the costs of the Mifeprex®, misoprostol, and associated dispensing fees at Kaiser, University of Washington, and Planned Parenthood Tacoma.

## 18.5 Publications

The preparation and submittal for publication of manuscripts containing the study results shall be in accordance with a process determined by mutual written agreement among the study PI and participating institutions. The publication or presentation of any study results shall comply with all applicable privacy laws, including, but not limited to, the Health Insurance Portability and Accountability Act of 1996.

[name]
Statistical Analysis Plan
ALTERNATIVE PROVISION OF MEDICATION ABORTION
VIA PHARMACY DISPENSING

Protocol Number:	17 - 22014
Version Date:	May 1, 2021
Investigational Product:	Mifeprex® ®
IND Number:	137073
Development Phase:	Phase 4 (post-marketing)
Sponsor:	[name] [name]
Funding Organization:	Fidelity Charitable
Principal Investigator:	Name: [name] [contact] [contact] E-mail: [contact]
Medical Monitor:	Name: [name] [contact] [contact] E-mail: [contact]
Coordinating Center:	UCSF

STATISTICAL ANALYSIS PLAN

1. Study Design

We will conduct a prospective cohort study of patients receiving Mifeprex® dispensed by pharmacists after undergoing standard clinical evaluation. Women participating in this study will obtain Mifeprex® and misoprostol from the pharmacy instead of in the clinic. All clinical procedures will continue to be performed as they currently are. The only difference is that the Mifeprex® will be dispensed by a pharmacist in the study pharmacy rather than by the clinician in the clinic. In particular, patients will be evaluated for all contraindications to the method according to the label, and they will sign the Patient Agreement Form. A clinician who has completed the Prescriber Agreement Form will write a prescription for Mifeprex® 200 mg for the eligible patient. The patient will then go to a designated pharmacy to fill the prescription, where it will be dispensed by a trained pharmacist. The patient will then take the Mifeprex® at the time indicated by the prescribing clinician. Patients will be contacted on Day 2 and Day 14 to complete surveys about their experience, and they will undergo standard clinical follow-up. In addition, we will perform surveys and interviews with pharmacists before and after initiating the study, as well as monitor the number of pharmacists who refuse to dispense Mifeprex® at the study pharmacies.

2. Aims and Objectives

The proposed study aims to investigate the feasibility, acceptability, and effectiveness of pharmacy dispensing of Mifeprex®; safety data will also be collected.

Our primary objective is to assess the feasibility of pharmacist dispensing of Mifeprex® by measuring pharmacist satisfaction and the proportion of pharmacists who refuse to dispense the medication to patients.

Secondary objectives include assessing patient satisfaction with the pharmacy-dispensing model; describing clinical outcomes, including effectiveness and adverse events, with pharmacist-dispensed Mifeprex®; and comparing pharmacist knowledge about medication abortion before and after the intervention.

3. Analyses

3.1 Patient arm

We will examine three outcomes related to patient participants' clinical experience and satisfaction with the pharmacist dispensing model. These will include two clinical outcomes: 1) effectiveness of medication abortion and 2) adverse events, as well as an outcome from the patient perspective: 3) satisfaction with the pharmacy experience at day 2. Effectiveness of medication abortion is defined as the proportion of participants who have a complete abortion with medications alone and do not undergo vacuum aspiration. Given the accuracy of patient self-assessment of abortion completion, we will use self-reported survey data to document

abortion outcome if the participant does not have follow-up contact with the clinic. Adverse events will be captured up to 6 weeks after participants are recruited into the study, and any ongoing adverse events will be followed until resolution. Adverse events are defined as serious using the FDA criteria and include death, hospitalization, blood transfusion, and surgery. Information about adverse events will be collected from abstracted data from patients' charts and self-reported data in patients' surveys. The satisfaction outcome will be based on participants' ratings on a Likert scale. On the day 2 survey, we ask participants "Overall, how satisfied were you with your experience at the pharmacy when you got the abortion pill?" with response options "Very satisfied," "Somewhat satisfied," "Somewhat dissatisfied," and "Very dissatisfied." We will dichotomize responses by those who report being very satisfied compared with all other responses. All demographic variables and pharmacy experience responses will be collected from patient surveys except gestational age at the clinic visit, which will come from clinical charts. Missing survey data for age, race and ethnicity, and parity will be obtained from patients' clinical chart data when available. We will conduct all analyses using Stata 15 and report significance at $P < .05$.

3.2 Pharmacist Arm

We will examine two primary outcomes and one secondary outcome related to the pharmacist dispensing model. Primary outcomes will include: 1) pharmacists who object to dispensing Mifeprex® and 2) pharmacists who report satisfaction with pharmacy dispensing of Mifeprex®, and the secondary outcome will be: 3) pharmacists' knowledge related to medication abortion.

Number of pharmacists who object to participate in dispensing Mifeprex® will be based on information reported by pharmacy managers and site research staff as well as pharmacists' who self-report objecting to dispensing Mifeprex® in their baseline survey. Pharmacy managers and site research staff will track pharmacists' participation in the training and Mifeprex® dispensing and report the number of pharmacists who refuse to dispense Mifeprex® to the coordinating study team. Using these data, we will calculate the proportion of pharmacists who refuse to dispense Mifeprex® during the study.

Number of pharmacists who report being satisfied with pharmacy dispensing of Mifeprex® will be based on survey data reported by pharmacists. At follow-up, we will assess satisfaction with pharmacy dispensing of Mifeprex® (ranging from very satisfied to very unsatisfied).

Difference in pharmacists' mean knowledge score related to medication abortion will be based on data collected in pharmacists' baseline and endline surveys. Knowledge scores will be based on a set of 15 items related to medication abortion for which respondents will select answers from multiple choice response options. Topics include medication abortion dosing regimen, biological processes during medication abortion, clinical outcomes, and federal and state policies relating to medication abortion. For pharmacists who complete at least 50% of the items, we will calculate their average number of correct responses among completed items. All questions or statements include an "I don't know" response option, which we will code as incorrect.

We will first assess the internal consistency reliability of the 15 knowledge items and consider a Cronbach's alpha coefficient above .70 to be acceptable to examine the items as a combined score.¹⁹ We will run descriptive summary statistics for baseline responses describing participant characteristics, as well as follow-up responses on satisfaction with the model. We will conduct a

series of multivariable logistic and linear regression analyses using Generalized Estimating Equation (GEE) models to assess whether study implementation is associated with pharmacists' overall medication abortion knowledge and on 15 individual medication abortion topics, ease and support of pharmacist dispensing of Mifeprex®. Coefficients in adjusted analyses examining overall medication abortion knowledge will represent the difference in mean knowledge scores between baseline and follow-up. We will conduct analyses in Stata 15.1 (StataCorp, College Station, TX).

We will also assess perceived benefits and challenges of pharmacist mifepristone dispensing. For perceived benefits, we will ask if this model “may improve access for women”, “expands pharmacists’ role in providing reproductive health services”, and “may streamline delivery of medications”, coding as dichotomous outcomes (yes/no). We will assess perceived ease of model implementation at baseline (anticipated ease) and follow-up (experienced ease) and personal support for pharmacist dispensing of mifepristone, measured on a four-point Likert scale, but coded dichotomously. We will code ease of implementation as very easy vs. somewhat easy/somewhat difficult/very difficult, and personal support for pharmacist dispensing of mifepristone as very supportive vs. somewhat supportive/somewhat unsupportive/very unsupportive.

For challenges, we will examine both anticipated (baseline) and experienced (follow-up) challenges (for example, lack of familiarity with medication or support from other pharmacists). At follow-up, we will assess how sufficient the medication abortion training and resources of the training were perceived to be (ranging from very sufficient to very insufficient), as well as satisfaction with pharmacy dispensing of mifepristone (ranging from very satisfied to very unsatisfied).

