Pharmacist participants will include any pharmacist working at one of the study pharmacy sites during the study who is willing to participate in the study. All pharmacists employed at the pharmacy sites will have a choice about participating in the research in terms of dispensing mifepristone and receiving the training, and in terms of completing the interviews/surveys. We have confirmed that there is at least one pharmacist at the site who is willing to dispense mifepristone. The baseline survey asks pharmacists if they plan to dispense mifepristone during the study. This will alert the research team if any pharmacists at a site say they do not plan to dispense, however, the research team will keep this information confidential. All pharmacists will be invited to the initial study training which will take place after baseline data collection. Pharmacists will be told that in order to dispense mifepristone they must receive the study training. (Remote training can be provided for interested pharmacists who were not able to attend the in-person session.) By knowing the number of pharmacists who have been trained and the total number of pharmacists that work at each site, we will have an idea of how many pharmacists will not be participating in the study dispensing. All trainings for pharmacists will include schedule mapping among participants to ensure that trained pharmacists are available to dispense to study participants during business hours. At the end of the training, pharmacists will be asked again whether they plan to dispense mifepristone during the study, as a check to assess whether sites may have any scheduling issues. We may also follow up with a lead pharmacist or pharmacy manager to confirm availability of trained pharmacists and work out a system for ensuring mifepristone is available to patients. We will conduct periodic check ins with the pharmacy manager/lead pharmacist since pharmacy staffing throughout the study period may fluctuate. Any new pharmacists will be reached with the study consent and baseline survey and the research team will provide training to interested pharmacists (remote training as needed). Our periodic check-ins can also assess how smoothly the study is running at the pharmacy and whether any pharmacists

have expressed concerns about or hesitation to dispense mifepristone.

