## 8.2 Method of Recruitment for Pharmacists

All pharmacists at the study pharmacies will be eligible. Pharmacists will be invited to participate in the survey/interview prior to initiating the study and at the end of the study by email/flyer and through face-to-face visits by study staff (see draft email in Appendix D). We will obtain the email addresses of pharmacists when we visit the pharmacy to introduce and launch the study. Pharmacists will voluntarily provide their email addresses. All pharmacists employed by the pharmacy sites will have a choice about participating in the research in terms of dispensing mifepristone and receiving the training, and in terms of completing the interviews/surveys. In the baseline survey, they will be asked whether they plan to dispense mifepristone when the pharmacy begins offering it. All pharmacists will be invited to a training and study launch to take place at their pharmacy. The training/study launch will involve the UCSF PI and/or site PI and research team presenting an overview of medication abortion and the aims and procedures of the study. They will also receive a binder of resource materials for the study, which they can refer to for further information throughout the study period.

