A pharmacist can participate in up to two surveys (baseline and endline) and two interviews (baseline and endline) but may decline to participate in any. We expect that there may be staffing changes from the beginning of the study to the end, so some may participate only in baseline data collection or only endline data collection. The survey includes a question asking if pharmacists would be willing to participate in an interview. Only those who respond "yes" will be contacted for interviews. The informed consent (Appendix E) will be used at beginning of the study to describe all of the study activities, including the baseline survey and interview, the endline survey and interview, and the training and dispensing. The consent will be used again at the end of the study before the endline survey and interview. The consent document for the pharmacists will not record the pharmacists' names or the names of the pharmacy, however we will program the surveys so that each pharmacy has a different link. This is how we will know which pharmacy respondents are from. It will also alert us if someone from a certain pharmacy does NOT consent to the training (identifying possible scheduling needs at this site). While not linked with survey responses, we do also collect email in the pharmacy survey in order to send a gift card. We have added a question asking if it is okay to contact them with details about the study training.

The consent includes language asking if pharmacists consent to audio recording of the interview. Since the interview may not happen immediately after the consent, we will confirm and document that pharmacists consent to audio recording before beginning the interview. Pharmacists can still participate in the study even if they decline the audio recording. Interviews will be scheduled at a convenient time when they do not interfere with the pharmacists' work.

The consent will also include description of the training and ask whether the pharmacist consents to the training.

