## 11.2 Monthly Assessments

Each month after initiating the study, research staff at UCSF will contact the supervising pharmacist at each pharmacy site to assess the number of pharmacists working at the site, whether any pharmacist has started to dispense Mifeprex®, and whether any pharmacist has stopped dispensing Mifeprex®.

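### Does the primary refusal proportion risk counting the same pharmacist twice because no key between its sources is stated?

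*SAP*

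**What the plan says.** SAP 3.2 makes refusal to dispense and satisfaction with dispensing the two primary pharmacist outcomes. For refusal, managers and site research staff follow who trains and who dispenses, and they "report the number of pharmacists who refuse to dispense Mifeprex® to the coordinating study team". Pharmacists "who self-report objecting to dispensing Mifeprex® in their baseline survey" are the other source. Then: "Using these data, we will calculate the proportion of pharmacists who refuse to dispense Mifeprex® during the study".

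Other sections bear on how these sources could be joined:

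- **Protocol 11.2:** a monthly contact with the supervising pharmacist "to assess the number of pharmacists working at the site, whether any pharmacist has started to dispense Mifeprex", and whether any has stopped.
- **Protocol 8.2:** at baseline "they will be asked whether they plan to dispense mifepristone when the pharmacy begins offering it". Consents carry no names, email is kept apart from the answers, and "we will program the surveys so that each pharmacy has a different link".
- **Protocol 6.1:** if pharmacists say at baseline that they do not plan to dispense, the team is alerted; "however, the research team will keep this information confidential". After training, "pharmacists will be asked again whether they plan to dispense mifepristone during the study". The team will know how many are trained and how many work at each site, and only trained pharmacists may dispense.
- **Protocol 11.3:** the endline survey asks whether the respondent refused at any time, and why.
- **Protocol 17.7 and 18:** subjects' documentation carries site number, subject number and initials, and all data collection forms carry a coded number and initials. The synopsis counts 50 pharmacists as subjects.
- **Protocol 16.3:** refusal is a calculated proportion, with no test or success threshold attached.

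The SAP compares baseline with follow-up by GEE and names no cluster unit.

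**The concern.** The managers' report is described as a number, and a number cannot be matched to individual survey answers. The pharmacist-specific text in Protocol 8.2 describes a link per pharmacy, not per person. Asking a manager to confirm names would cut across the confidentiality promised in Protocol 6.1. The baseline answer is also a plan stated before training, while the outcome is refusal during the study, so an objector who later dispenses could stay in the count.

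If overlap between the sources were never recorded, the number of refusers could only be bounded. In the worst case the proportion doubles, and it is a headline feasibility result. Without a person-level key, the two survey waves could not be paired for the knowledge comparison either.

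**Working it through.** The plan states no figure for this outcome, so there is none to reproduce. The documents give only a ceiling of 50 pharmacists (Protocol 16.6) and six sites (Protocol 5). The refuser counts, catch rates and correlations below are assumptions.

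**1. Bounds if nothing can be matched.** With M refusers reported by managers and staff and S by survey, distinct refusers lie between max(M, S) and M + S. With N = 50:

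| M, S | Distinct refusers | Proportion | Exact 95% interval at each end |
|---|---|---|---|
| 3, 3 | 3 to 6 | 6% to 12% | 1.3-16.5% and 4.5-24.3% |
| 5, 3 | 5 to 8 | 10% to 16% | 3.3-21.8% and 7.2-29.1% |
| 5, 5 | 5 to 10 | 10% to 20% | 3.3-21.8% and 10.0-33.7% |

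The pharmacy-specific link lets these bounds be taken pharmacy by pharmacy. The count is exact wherever one source reports zero.

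**2. What each counting rule gives.** Let 5 of 50 refuse (10%), and let the sources catch each refuser independently with probabilities a and b. The expected proportions are:

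- distinct people: 10% × [1 − (1 − a)(1 − b)]
- simple addition: 10% × (a + b)

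| a, b | Distinct people | Addition |
|---|---|---|
| 0.6, 0.6 | 10% × (1 − 0.16) = 8.4% | 12% |
| 0.6, 0.9 | 10% × (1 − 0.04) = 9.6% | 15% |
| 0.9, 0.9 | 10% × (1 − 0.01) = 9.9% | 18% |

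Taking the larger count within each pharmacy needs no person-level key. Simulated with pharmacies of 8, 8, 8, 8, 9 and 9 staff, it gives 8.1-9.9%.

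**3. Objectors who later dispense.** Let a quarter of the 5 dispense after all, so the truth is 3.75/50 = 7.5%. The survey (probability a) can catch all 5; managers (probability b) can catch only the 3.75 who go on refusing.

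- Distinct people, 0.6 and 0.6: (3.75 × 0.84 + 1.25 × 0.6)/50 = 3.90/50 = 7.8%.
- Distinct people, 0.9 and 0.9: (3.75 × 0.99 + 1.25 × 0.9)/50 = 4.84/50 = 9.7%.
- Addition, 0.6 and 0.6: (3.75 × 1.2 + 1.25 × 0.6)/50 = 5.25/50 = 10.5%.

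Across steps 2 and 3, counting distinct people misses the truth by 1.6 points low (8.4 against 10) to 2.2 points high (9.7 against 7.5). For scale, the exact interval for 5/50 spans 18.5 points.

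**4. Which rule the text supports.** The SAP speaks of the number and proportion of pharmacists, which is a count of people. No section says the sources are summed. Staff are said to follow individuals' training and dispensing, so the number they pass on comes from a record that may well identify people. With about 50/6 ≈ 8 pharmacists per pharmacy (one pharmacy per site assumed), a coded number or initials would settle most overlaps. The coordinating team receives both sources, so it can do the matching without telling the manager anything.

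**5. GEE.** In SD units, with n = 50 in both waves, the standard error of the change is √(2(1 − ρ)/n) if waves are linked and √(2/n) = 0.200 if not. For ρ = 0.3, 0.5 and 0.7 the linked values are 0.167, 0.141 and 0.110. Treating the waves as unlinked therefore loses precision but does not create false positives. In simulations (50 per wave, six pharmacies, intraclass correlation 0.05), taking the pharmacist as unit with pharmacy fixed effects gave 5-6% type I error, or 7-11% if the true change varied between pharmacies. Rates of 13-18% arose only from an uncorrected pharmacy-level robust z-test, which the SAP does not specify.

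**The case for a change.** The strongest reply is that a code on the surveys does not help if the other source arrives as a bare count, and both SAP 3.2 and Protocol 11.2 describe counts. Protocol 8.2 is specific to pharmacists and mentions only a pharmacy link, while the coded-number rules in 17.7 and 18 are general. Double counting would be a systematic upward error that no confidence interval covers.

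Part of this stands. The merge rule, the handling of objectors who later dispense, and the denominator are all unwritten, and the general and specific passages sit uneasily together. The denominator could be all staff (Protocol 6.1 and 11.2) or those completing a survey or interview (Protocol 16.1); 5 refusers are 10% of 50 but 12.5% of 40.

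The step from unwritten to impossible does not stand. The survey forms are in appendices that are not part of the reviewed documents, so the absence of a code field cannot be shown, and a number passed upward does not show that the site record lacks identities. If matching did prove impossible, the sources could be reported side by side with the bounds in step 1, and the endline question on actual refusal gives a further check.

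**Conclusion.** No change to the plan follows. The gap is real but is one of detail, and analysts would fill it sensibly: count each pharmacist once, judge refusal during the study by what was done rather than by a baseline plan, and state the staff denominator alongside the result. On the assumed inputs, even the plain union, with later dispensers left in, comes within about 2 points of the truth, which is small beside an exact interval of 3.3-21.8% for 5 of 50. The figures of 12-18% require adding the sources, a rule the SAP does not state.

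The outcome is descriptive and has no threshold, so no stated decision turns on the difference. The GEE point is smaller still: it is secondary, and the natural repeated unit is the pharmacist. These conclusions rest on assumed counts, on catch rates of 60-90% acting independently, and on the coded number in Protocol 17.7 and 18 applying to pharmacists. If that last assumption fails, the result is a bounded range rather than a single figure.

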### 3.2 Secondary Objectives

The secondary objectives include to assess patient satisfaction with the pharmacy-dispensing model, to describe clinical outcomes, and to compare pharmacist knowledge about medication abortion before and after the intervention. Secondary outcomes include patient satisfaction with the pharmacy-dispensing model; clinical outcomes, including effectiveness and adverse events, with pharmacist-dispensed mifepristone; and pharmacist knowledge about medication abortion before and after the intervention.

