### 16.1 Data Sets Analyzed

All eligible patients who receive the dose of the study drug will be included in the analysis. All eligible pharmacists who complete at least one survey or interview will be included in the pharmacist analysis.

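### Does the before/after pharmacist knowledge comparison confuse learning with staff turnover because SAP 3.2 leaves the GEE settings unstated?

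*SAP*

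**What the plan says.** Comparing knowledge across the study is a secondary objective: Protocol section 3.2 sets out "to compare pharmacist knowledge about medication abortion before and after the intervention".

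On who is analysed, Protocol section 16.1 states: "All eligible pharmacists who complete at least one survey or interview will be included in the pharmacist analysis". Section 8.2 anticipates staff changes, "so some may participate only in baseline data collection or only endline data collection". Section 6.1 adds for later arrivals: "Any new pharmacists will be reached with the study consent and baseline survey". Section 16.6 caps the pharmacist sample at 50, set by staffing and not by a calculation.

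On the model, SAP section 3.2 specifies "multivariable logistic and linear regression analyses using Generalized Estimating Equation (GEE) models" and interprets the result: "Coefficients in adjusted analyses examining overall medication abortion knowledge will represent the difference in mean knowledge scores between baseline and follow-up". Its only filter on the knowledge score is that at least half of the 15 items be completed. It gives no cluster unit, working correlation, variance estimator or covariate list, and no analysis of pharmacists with both surveys.

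On matching the two surveys, Protocol section 8.2 says of the pharmacy-specific survey links, "This is how we will know which pharmacy respondents are from", and of contact details, "While not linked with survey responses, we do also collect email in the pharmacy survey in order to send a gift card". Sections 17.7 and 18 refer to subject or coded numbers on study forms.

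**The concern.** A GEE is not fully determined until the cluster and the working correlation are chosen. When the two waves contain partly different people, the working correlation moves the point estimate as well as the interval. If those who leave know less at baseline than those who stay, mean knowledge rises between waves even when nobody learns anything. A reader could then credit the training with an effect that is partly turnover, and two analysts following the same text could report different numbers. The same models also serve the 15 single topics, ease of implementation and personal support. If the two surveys could not be matched by person, clustering on the pharmacist would not be possible at all.

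**Working it through.** The plan gives no sample size, effect size or power for the knowledge comparison, so there is no figure to reproduce. The check is an illustration on assumed inputs, in an unadjusted linear model.

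**Inputs.** From the documents: up to 50 pharmacists (Protocol 16.6). Assumed: n = 50 at baseline; a share f with no endline survey, so m = 50(1 − f) pairs; leavers score d SD below stayers at baseline; score SD 1; within-person correlation ρ = 0.5; no true learning. Endline-only respondents are set to zero because new staff are offered a baseline survey.

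**Differences between estimates.**
- Independence minus complete pairs = f × d. With f = 0.4 and d = 0.5 this is 0.20 SD; with f = 0.2 and d = 0.25 it is 0.05 SD.
- Independence minus exchangeable = ρ × f × d = 0.10 SD and 0.025 SD.

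**Standard errors at f = 0.4 (m = 30).**
- Independence: √(1/n + 1/m − 2ρ/n) = √(0.0200 + 0.0333 − 0.0200) = 0.183.
- Exchangeable: √((1 − ρ²)/m + ρ²/n + 1/n − 2ρ/n) = √(0.0250 + 0.0050 + 0.0200 − 0.0200) = 0.173.
- Complete pairs: √(2(1 − ρ)/m) = √(1/30) = 0.183.

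**False rejection at |z| > 1.96, no learning.** The bias depends on why people leave. If leaving follows a stable trait, the biases are f × d, (1 − ρ) × f × d and 0. If it follows the baseline score itself, they are ρ × f × d, 0 and −(1 − ρ) × f × d, because the pairs regress to the mean.

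| Case | Reason for leaving | Independence | Exchangeable | Complete pairs |
|---|---|---|---|---|
| f = 0.4, d = 0.5: bias | trait | 0.20 | 0.10 | 0 |
| rejection | trait | 0.195 | 0.089 | 0.050 |
| f = 0.4, d = 0.5: bias | baseline score | 0.10 | 0 | −0.10 |
| rejection | baseline score | 0.085 | 0.050 | 0.085 |
| f = 0.2, d = 0.25: rejection | trait | 0.062 | 0.053 | 0.050 |
| f = 0.2, d = 0.25: rejection | baseline score | 0.053 | 0.050 | 0.053 |

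Complete pairs does best in one mechanism and shares the worst place in the other; exchangeable does the reverse or sits between. If leavers and stayers do not differ (d = 0), independence and exchangeable still disagree by chance, with SD √(0.0333 − 0.0300) ≈ 0.06, about a third of the standard error.

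**Cluster unit.** Assume all 50 answer both waves, six near-equal pharmacies and a true change of 0.5 SD.
- No pharmacy-by-wave variation: variance of the change = 2(1 − ρ)/50 = 0.020, SE 0.141. Power is about 94% clustered on pharmacist and about 80% for a pharmacy-clustered t test on 5 df; simulation gave 94–95% and 81–82%.
- Pharmacy-by-wave variance 0.05 in each wave: variance = 0.020 + 2 × 0.05/6 = 0.0367, SE 0.191. Type I error clustered on pharmacist rises to about 15% (simulation 15–18%, the higher value with unequal pharmacies). The pharmacy-clustered t test stays at 5–7%, but its power falls to about 56% (simulation 56–58%).

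So the cluster unit trades error control against power, and 81–82% overstates the pharmacy-clustered test's power in the one setting that would call for it.

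**Matching of surveys.** Set side by side, Protocol sections 8.2, 17.2, 17.7 and 18 do not conflict. Emails kept apart from responses and identifiers stored separately are both compatible with a coded number on each form. The survey instruments and consent are not supplied, so the documents show neither that a person-level code exists nor that it is absent.

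**The case for a change.** The strongest case for a change is that the sponsor itself expects single-wave respondents, that the SAP was the place to say how they enter the model, and that a few sentences would remove the ambiguity. GEE does not cure the problem: in the stable-trait case an exchangeable structure leaves half of the bias, and it needs person-level pairing that the documents do not describe. Naming the settings and showing the complete-pairs result would cost little.

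What stands is that the settings are unstated and that the estimate depends somewhat on them. What does not stand is that the inclusion rule is wrong. SAP 3.2 promises a difference in mean scores between waves, not change within the same individuals, and an available-data analysis answers that question. Preferring the within-person quantity means preferring a different estimand. The proposed additions also fail in some of the scenarios offered in their support: complete pairs are biased by −0.10 SD when leaving follows the baseline score, and the pharmacy-clustered test is weak with six clusters. The illustration is unadjusted, whereas the plan specifies multivariable models, so its biases are not those of the planned analysis. Some handling of turnover is already in place: new staff are offered a baseline survey (Protocol 6.1), and the number of pharmacists at each site is checked monthly (Protocol 11.2).

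**Conclusion.** No change is needed. This is missing modelling detail in a secondary, uncontrolled before/after comparison of at most 50 pharmacists, and the choices left open are trade-offs. An analyst would ordinarily cluster on pharmacist where surveys can be matched, use robust standard errors, report how many people answered each wave, and describe the result as two cross-sections where they cannot be matched. Nothing in the plan prevents this.

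The possible distortion runs from negligible (5–6% false rejection under every option with 20% lost and a 0.25 SD gap) to material (19% under independence with 40% lost, a 0.5 SD gap and trait-driven leaving). That range rests wholly on assumed values for loss, score gap and correlation; the documents support no particular point in it. The refusal and satisfaction outcomes, which carry the primary objective, do not depend on the knowledge models. The conclusion would weaken if a large share of baseline respondents had left by the endline survey and the report still presented the coefficient as learning by the same individuals.
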